## **14.2. Tumor Tissue**

MHC-II testing for treatment assignment will be tested using archival tissue obtained since last systemic therapy or using fresh biopsies. Fresh biopsies prior to treatment will be obtained whenever possible, even if archival tissue is available. Available tissue will also be tested for RNA sequencing, immunofluorescence testing (including PD-L1, CD8, CD4, and others).

When at all reasonably possible, the same archival tissue originally used for initial screening should also be used for additional correlative analysis. Fresh biopsies are still encouraged even if sufficient archival tissue for MHC-II testing is available.

If residual archival tumor tissue is unavailable or insufficient from the time point previously used for initial MHC-II testing, then alternative tissue from the most recent biopsy/specimen should be used for correlative research.

Every reasonable effort should be made to obtain additional pre-treatment archival slides to assess tumor heterogeneity and dynamic changes over time.

## **14.3. Peripheral Blood**

Blood from each patient at Pre-Treatment (C1D1), On-Treatment (as specified in section 7), and at EOT/Progression is **required**. Subjects who discontinue study related therapy can continue to have correlative blood samples collected.

Approximately 47mL of peripheral blood is anticipated to be drawn for correlative research at each of 7 time points in Study Arm A and Study Arm B: c1d1, c1d15, c2d15, c4d1, c14d1, EOT, and 30d F/U (Arm A); and c1d1, c1d15, c3d1, c5d1, c15d1, EOT, and 30d F/U (Arm B).

## **14.4. Specimen Banking**

Any leftover study tissue or blood samples may be stored for future research studies. The subjects will consent to the future use of samples in the consent form for the study. All future use as part of residual or repository specimens collected in this trial for purposes not prospectively defined will require review and approval by the Institutional Review Board according to its established policies, whether the specimens are stored in a central site or at a local institution or in a virtual repository.

# **15. DATA SAFETY AND MONITORING**

## **15.1. Data Management and Reporting**

Participating institutions will be collaborating with Vanderbilt for patient accrual. Data will be collected using a centralized electronic case report form called ON-line Clinical Oncology Research Environment = Oncore (<http://www.vicc.org/ct/research/oncore.php>). Oncore is a highly secure, web based, cancer specific, and customizable system that provides fully integrative clinical

data management and study administration capabilities developed in an ongoing collaborative effort with NCI designated Comprehensive Cancer Centers. It fully integrates study administration functionality including protocol tracking, patient registration, NCI reporting, review committee tracking, and SAE tracking, with clinical data management functionality including electronic case report forms (eCRF) design, clinical data capture, protocol and regulatory compliance monitoring. Also the system is capable of storing basic protocol information (e.g., IRB approval dates, dates for annual renewals) and clinical trial research data. Oncore allows the investigator to define specific protocol requirements and generate data collection forms. Creation of the data collection form is done with a single button click after the parameters of an individual protocol have been specified. Oncore permits specification of study protocols, management of patient enrollment, clinical data entry and viewing, and the generation of patient or study-specific reports based on time stamping. OnCore is embedded with a comprehensive domain repository of standard reference codes and forms to promote standardization. The sources for the repository include CDUS, CTC, CDEs from NCI, ICD, MedDRA and various best practices from contributing NCI-designated Comprehensive Cancer Centers. OnCore provides several reporting features specifically addressing NCI Summary 3 and Summary 4 and other reporting requirements. Data may also be exported in a format suitable for import into other database, spreadsheets or analysis systems (such as SPSS). This system will be used to manage all VICCC clinical trials data. OnCore is maintained and supported in the VICC Clinical and Research Informatics Resource.

## **15.2. Meetings**

This study will be monitored by the VICC melanoma research team, which includes medical oncologists, research nurses, data managers, and regulatory specialists. The team meets on a regular basis to discuss AEs/SAEs, accrual, compliance, safety issues, adherence to protocol, etc. pertaining to cancer studies conducted by the team. In addition, meetings between the Coordinating Center and research teams at participating sites may be scheduled as necessary, in order to discuss relevant issues related to the trial (e.g. AEs/SAEs, accrual, compliance, safety issues, adherence to protocol, reviews).

## **15.3. Monitoring**

The Vanderbilt-Ingram Cancer Center (VICC) oversees patient safety and data monitoring for its investigator-initiated and NIH-NCI funded clinical trials through its Data and Safety Monitoring Committee (DSMC). The purpose of the DSMC is to ensure the efficient implementation and management of the VICC Data and Safety Monitoring Plan (DSMP). The Committee maintains authority to intervene in the conduct of studies as necessary to ensure clinical research performed at VICC achieves the highest quality standards.

The VICC DSMC meets on a quarterly basis and ad hoc to discuss data and safety monitoring of clinical trials and to oversee the VICC DSMP. Internal audits for compliance with adverse event reporting, regulatory and study requirements, and data accuracy and completion are conducted according to the VICC DSMP according to study phase and risk. The committee reviews all serious adverse events (SAE) on Vanderbilt sponsored investigator-initiated studies on a quarterly basis and provides DSMC SAE review reports to the Vanderbilt IRB.

## **15.4. Data Handling and Record Keeping**

An electronic case report form (eCRF) is required and must be completed for each included participant. The completed dataset should not be made available in any form to third parties, except for authorized representatives of appropriate Health/Regulatory Authorities, without written permission from Vanderbilt.

To enable evaluations and/or audits from health authorities and Vanderbilt, each site investigator agrees to keep records including: The identity of all participants (sufficient information to link

---

records; e.g., hospital records), all original signed informed consent forms, copies of all source documents, and detailed records of drug disposition. To comply with international regulations, the records should be retained by the investigator in compliance with regulations.

Queries resulting from review of the eCRFs will be generated for the site and corrections will be made by the study site personnel. This will be done on an ongoing basis.

## **16. REGULATORY CONSIDERATIONS**

### **16.1. Protocol Review and Amendments**

Information regarding study conduct and progress will be reported to the Institutional Review Board (IRB) per current institutional standards at each participating study site.

The trial will not be initiated until there is approval by the local IRB of the protocol, informed consent document and any other material used to inform the patient about the nature of the trial. The IRB should be duly constituted according to local regulatory requirements. The investigator will inform the IRB of the progress of the trial at least yearly.

Any changes to the protocol will be made in the form of a written amendment and must be approved by the sponsor-investigator and the IRB of each institution prior to local implementation. All amendments will also be submitted as necessary to the FDA by the sponsor-investigator (or designee).

Protocol changes to eliminate an immediate hazard to a trial patient may be implemented by the investigator immediately. The investigator must then immediately inform the local IRB; and the sponsor-investigator (or designee), who will communicate as appropriate with the FDA.

The sponsor-investigator (or designee) is responsible for the coordination and development of all protocol amendments. Once approved by the sponsor-investigator, Vanderbilt will disseminate this information to the participating centers.

### **16.2. Informed Consent**

The investigator (or designee) will explain to each subject the nature of the study, its purpose, the procedures involved, the expected duration, the potential risks and benefits involved and any discomfort it may entail. Each subject will be informed that participation in the study is voluntary, that s/he may withdraw from the study at any time, and that withdrawal of consent will not affect subsequent medical treatment or relationship with the treating physician(s) or institution. The informed consent will be given by means of a standard written statement, written in non-technical language, which will be IRB approved. The subject should read and consider the statement before signing and dating it, and will be given a copy of the document. No subject will enter the study or have study-specific procedures done before his/her informed consent has been obtained.

In accordance with the Health Information Portability and Accountability Act (HIPAA), the written informed consent document (or a separate document to be given in conjunction with the consent document) will include a subject authorization to release medical information to the study sponsor and supporting agencies and/or allow these bodies, a regulatory authority, or Institutional Review Board access to subjects' medical information that includes all hospital records relevant to the study, including subjects' medical history.

### **16.3. Ethics and GCP**

This study will be carried out in compliance with the protocol and Good Clinical Practice, as described within:

1. ICH Harmonized Tripartite Guidelines for Good Clinical Practice 1996.
2. US 21 Code of Federal Regulations dealing with clinical studies (including parts 50 and 56 concerning informed consent and IRB regulations).
3. Declaration of Helsinki, concerning medical research in humans (Recommendations Guiding Physicians in Biomedical Research Involving Human Subjects, Helsinki 1964, amended Tokyo 1975, Venice 1983, Hong Kong 1989, Somerset West 1996).

The investigator agrees to adhere to the instructions and procedures described within the above and thereby to adhere to the principles of Good Clinical Practice with which the above conform.

### **16.4. Confidentiality**

It is the responsibility of the investigator to ensure that the confidentiality of all patients participating in the trial and all of their medical information is maintained. Case report forms (CRFs) and other documents submitted to regulatory authorities must not contain the name of a trial patient. All patients in the trial will be identified by a unique identifier which will be used on all CRFs and any other material submitted to regulatory authorities. All case report forms and any identifying information must be kept in a secure location with access limited to the study staff directly participating in the trial.

### **16.5. Study Termination**

The sponsor-investigator reserves the right to terminate the study at any site and at any time. Reasons for study termination may include, but are not limited to, the following:

- Investigator non-compliance with the protocol, GCP or regulatory requirements.
- Insufficient enrollment.
- Safety concerns.
- Decision by suppliers to modify or discontinue the availability, development or manufacture of protocol-indicated treatment.
- A request to discontinue the study by the IRB or FDA.

The sponsor-investigator will promptly notify investigators, the IRB and FDA if the study is terminated for any reason.

## **17. STUDY COORDINATION**

### **17.1. Trial Compliance**

This is an investigator-initiated study. The Principal Investigator, [name]. (who may also be referred to as the Sponsor-Investigator), is conducting the study as acting as the sponsor. Therefore, the legal and ethical obligations of the Principal Investigator include both those of a sponsor and those of a principal investigator.

Vanderbilt is the Coordinating Center for this study. All aspects of the study will be carefully monitored by the Coordinating Center for compliance with applicable government regulations with respect to current GCP and standard operating procedures.

### **17.2. Changes to Protocol and Informed Consent Document**

Any change to the protocol and informed consent document must be reviewed and approved by the Coordinating Center before being submitted to the Institutional Review Board/Independent Ethics Committee at participating institutions. Amendments should not be implemented until all necessary approvals have been obtained, except when necessary to eliminate an immediate hazard to study subjects.

### **17.3. Protocol Deviations**

The Coordinating Center is responsible for implementing and maintaining quality assurance and quality control to ensure that studies are conducted according to the protocol, GCP, and all applicable regulatory requirements. A protocol deviation is any noncompliance with the protocol. Noncompliance can be on the part of the study participant, the investigator, or the study site staff. Deviations to the protocol are not permitted except when necessary to eliminate an immediate hazard to study subjects.

### **17.4. Monitoring and Quality Assurance**

As the Coordinating Center, Vanderbilt has responsibilities to health authorities to take all reasonable steps to ensure the proper conduct of the study with regard to ethics, protocol adherence, integrity, validity of the data recorded on the CRFs, and adherence to regulations regarding Good Clinical Practice (GCP) and the protection of human subjects.

In accordance with applicable regulations, GCP, and Coordinating Center procedures, sites will be contacted prior to the start of the study to review with site staff the protocol, study requirements, and site responsibilities to satisfy regulatory, ethical, and Coordinating Center requirements.

During the course of the study, the Coordinating Center will routinely monitor the sites for protocol compliance, compare CRFs with original source documents from individual subjects, assess drug accountability, and ensure that the study is being conducted according to the pertinent regulatory requirements. The review of subject medical records will be performed in a manner to ensure that subject confidentiality is maintained. Monitoring visits will primarily be conducted remotely, and sites are required to provide the appropriate source documentation in order to allow for proper oversight per GCP. Investigators must agree to cooperate with the Coordinating Center to ensure that any problems detected are resolved.

### **17.5. Data Verification**

Data will be collected via eCRFs and entered into the database per Coordinating Center guidelines. The Coordinating Center will check data accuracy by performing source data verification. Source data verification is a direct comparison of the entries made on the CRFs against the appropriate source documentation. This will be conducted remotely, with the possibility of on-site verification periodically. Discrepancies in the data will be brought to the attention of the investigator and/or the investigator's staff. Any necessary corrections will be made directly to the eCRFs or via queries by the investigator and/or the investigator's staff.

### **17.6. Study Documentation**

Each participating site is responsible for submitting copies of all relevant regulatory documentation to the Coordinating Center. The required documents include, but are not limited to the following: local IRB approvals (i.e., protocol, consent form, amendments, patient brochures, recruitment material, etc.), each participant's informed consent, enrollment form, eligibility checklist, summary of unanticipated problems or protocol deviations, and documentation of expertise of the investigators. The Coordinating Center will provide each participating site with a comprehensive list of the necessary documents. Specified members at each participating site will submit all pertinent regulatory documents to the Coordinating Center, for storage in a secure location. It is the responsibility of the participating sites to maintain copies of all documentation submitted to the Coordinating Center.

### **17.7. Closure of the Study**

The Coordinating Center reserves the right to discontinue a site at any time during the study for medical or administrative reasons such as:

- Unsatisfactory enrollment;
- GCP noncompliance;
- Inaccurate or incomplete data collection;
- Falsification of records;
- Failure to adhere to the study protocol.

### **17.8. Records Retention**

U.S. FDA regulations (21 CFR §312.62[c]) require that records and documents pertaining to the conduct of this study and the distribution of investigational drug, including CRFs, consent forms, laboratory test results, and medication inventory records, must be retained by each Principal Investigator for 2 years after marketing application approval. If no application is filed, these records must be kept 2 years after the study is discontinued and the U.S. FDA and the applicable national and local health authorities are notified.

Following closure of the study, each participating center will maintain a copy of all site study records in a safe and secure location. The Coordinating Center will inform the investigator at each site at such time that the records may be destroyed.

### **17.9. Publication**

It is understood that any manuscript or releases resulting from the collaborative research must be approved by the sponsor-investigator and will be circulated to applicable participating sites/investigators prior to submission for publication or presentation.

## **18. STATISTICAL CONSIDERATIONS**

### **18.1. Primary Endpoint**

To evaluate the efficacy, measured by change in activated GZMB+ CD8+ T-cell density intratumorally, of two immunotherapy regimens in patients with advanced melanoma. Patients with MHC-II (+) melanoma receive nivolumab plus relatlimab treatment. Patients with MHC-II (-) melanoma receive nivolumab plus ipilimumab treatment.

### **18.2. Sample Size and Power**

The primary endpoint for this study is change in GZMB+ CD8+ T cell infiltration. A total sample size of 36 with 18 in each arm will provide 83% power to detect a difference in mean activated CD8+ T cell density change of one standard deviations (e.g., 1 SD=1000 counts/mm^2 is roughly the effect size for doubling T cell count), with a two-sided significance level of 0.05. Assuming a 10% dropout rate, a total number of 40 patients is planned for enrollment in the study to ensure the study has adequate statistical power for the primary analysis.

### **18.3. Secondary Endpoints**

Efficacy for each arm: response rate as measured by RECIST 1.1, progression free survival, and overall survival. Survival statistics will be assessed descriptively for each arm and summarized with median, 1 year, and 2 year landmark analyses.

Safety: safety and tolerability of nivolumab plus relatlimab in patients with MHC-II (+) melanoma, and of nivolumab plus ipilimumab in patients with MHC-II (-) melanoma.

### **18.4. Statistical Analysis Plan**

Patient demographics/other baseline characteristics will be listed by patient and/or summarized descriptively by each arm. Categorical data will be presented as frequencies and percentages. For continuous data, summary statistics will be presented. Between-group differences will be assessed with t-test based on a continuous variable. Nonparametric counterparts, Wilcoxon rank sum test, will be used when assumptions for parametric methods are not met. Binary and categorical data will be analyzed with chi-squared test or Fisher's exact test. Multivariable analysis will be performed using linear regression model, where the outcome variable is the density of activated CD8+ T cell post-treatment and the explanatory variable is the MHC-II status, adjusted for baseline T cell density. Median PFS and median OS will be estimated with 95% confidence intervals. If the median has not be reached by the end of the follow-up, mean survival will be reported instead. Kaplan-Meier curves will be constructed by MHC-II status. Multiple comparison issues will be corrected using the Bonferroni's approach. All statistical analysis will be performed using R 3.4.2 or a newer version.

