### **3.7. Rationale for Primary Endpoint**

The primary endpoint for this study is change in CD8+ T cell infiltration. Several studies have demonstrated influx of CD8+ T cells as demonstrating immunologic recognition and targeting, and as an early surrogate for treatment response. For example, one study demonstrated that expression of CD8 in early on-treatment biopsies was completely non-overlapping in responders compared with non-responders. Thus, this metric can serve as an accurate surrogate of immunologic recognition and tumor responses, and is likely more reliable than a metric such as complete pathologic response, particularly in the setting of bulky tumors that may require additional time for complete regression. In addition, in this signal finding phase II study, we are evaluating two arms with likely active treatments in parallel, rather than comparing these interventions. Sample size is further based on doubling of CD8+ T cell infiltration from analysis of responding patients in two studies, with a standard deviation of 1000.

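### The primary objective is the density change under each regimen, but the plan powers and tests only a between-arm contrast and plans no per-arm estimate with a confidence interval

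*Combined protocol and SAP*

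**What the plan says.** Sections 4 and 18.1 set the primary objective as the change in activated GZMB+ CD8+ density under each of two regimens, each given to a different MHC-II group. Section 3.7 says that "we are evaluating two arms with likely active treatments in parallel, rather than comparing these interventions".

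Section 18.2 gives 83% power, with 18 per arm and a two-sided 0.05 level, to detect "a difference in mean activated CD8+ T cell density change of one standard deviations". It takes 1 SD as 1000 counts/mm2, which it says "is roughly the effect size for doubling T cell count". Section 3.7 gives the same basis: "Sample size is further based on doubling of CD8+ T cell infiltration from analysis of responding patients in two studies".

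Section 18.4 lists these analyses:
- For comparing groups: "Between-group differences will be assessed with t-test based on a continuous variable".
- As a fallback, with no rule for when the assumptions count as failed: "Nonparametric counterparts, Wilcoxon rank sum test, will be used when assumptions for parametric methods are not met".
- A linear regression, its outcome and terms described as follows: "the density of activated CD8+ T cell post-treatment and the explanatory variable is the MHC-II status, adjusted for baseline T cell density".
- An interval estimate, for the survival endpoints only: "Median PFS and median OS will be estimated with 95% confidence intervals".

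Continuous data also receive summary statistics. No analysis is called primary, although Section 18.2 refers to one. No confidence interval or test is planned for the density change within an arm, and the scale of the change is not stated in the analysis section.

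**The concern.** The question and the inference do not match. A between-arm test of mean change asks whether one arm gained more than the other. If both regimens raise the density by the same amount, its expected result is null; if neither does anything, its expected result is also null. The two outcomes that matter most to the stated objective cannot be told apart by the powered test.

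A positive result would be hard to interpret too. Every MHC-II positive patient receives nivolumab plus relatlimab and every MHC-II negative patient receives nivolumab plus ipilimumab, so the MHC-II indicator in the regression is the arm indicator. Its coefficient mixes the regimen with the tumour type. The hypothesis that MHC-II is an effective stratifying marker (Section 3.8) could then appear to be supported by a contrast that cannot isolate it.

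Finally, with no primary analysis named, a t-test, a rank test and a regression that can disagree all remain available after the data are seen.

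**Working it through.** **1. The plan's own figure.** Inputs from Section 18.2: 18 per arm, difference 1 SD, two-sided 0.05. For a two-sample t-test the noncentrality is 1 × √(18/2) = 3 with 34 degrees of freedom, giving power 83.0%. The stated 83% reproduces. A one-sample t-test within an arm (n = 18, change of 1 SD, noncentrality √18 = 4.24, 17 degrees of freedom) would have 97.9%. The stated figure therefore belongs to the between-arm contrast on the raw change.

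**2. What that contrast shows.** Take 1000 counts/mm2 as the SD of change.

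| Mean change, Arm A | Mean change, Arm B | Difference | Rejection |
|---|---|---|---|
| 0 | 0 | 0 | 5% |
| +1000 | +1000 | 0 | 5% |
| +1000 | 0 | 1000 | 83% |

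The first two rows have opposite answers to the objective and the same test behaviour.

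**3. Per-arm precision.** Multiplier: t(0.975, 17)/√18 = 2.110/4.243 = 0.497.
- Absolute scale: with SD 1000, the 95% CI half-width is 0.497 × 1000 = 497 counts/mm2.
- Ratio scale: the CI is the observed ratio divided and multiplied by exp(0.497 × SD of the log ratio). The documents give no log-scale SD, so it is assumed here.

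| Assumed log-ratio SD | Factor | 95% CI around an observed ratio of 2.0 |
|---|---|---|
| 0.5 | 1.28 | 1.56 to 2.56 |
| 0.69 | 1.41 | 1.42 to 2.82 |
| 0.83 | 1.51 | 1.32 to 3.02 |
| 1.0 | 1.64 | 1.22 to 3.29 |

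**4. Scale.** A rise of 1000 is a doubling only from a baseline of 1000. From 250 it is 1250/250 = 5-fold; from 4000 it is 5000/4000 = 1.25-fold. The target in counts and its justification as a doubling therefore agree at one baseline only.

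**5. Why scale affects a between-arm test.** Section 3.5 describes MHC-II positive tumours as more infiltrated, so unequal baselines are plausible. It gives no densities, is not specific to GZMB+ CD8+ cells, and for MHC-II negative tumours it stresses CD4+ cells. Simulation, all settings assumed: lognormal densities, CV 0.7 to 1.0, 18 per arm, both arms truly doubling, 20,000 trials per setting. In model A the fold change is independent of baseline (log-ratio SD 0.5 to 0.83). In model B the log variance is equal before and after treatment (log correlation 0.3 to 0.7). Rejection at 0.05:

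| Test | Baseline gap | Model A | Model B |
|---|---|---|---|
| t-test, raw change | 2-fold | 11–29% | 14–42% |
| t-test, raw change | 1.5-fold | 6–12% | 8–18% |
| t-test, raw change | 1.25-fold | 4–6% | 5–8% |
| Rank-sum, raw change | 2-fold | 12–29% | 14–42% |
| Raw baseline-adjusted regression | 2-fold | 4–5% | 12–48% |
| t-test, log ratio | 2-fold | 5% | 5% |

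The rank-sum fallback gives no protection because it ranks absolute changes.

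**6. The mirror case.** If both arms gain the same absolute amount from unequal baselines (1000 to 2000 and 2000 to 3000), the log-ratio t-test rejects 13–41% and the raw-change t-test 3–5%. Each scale fails under the other's null.

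**The case against.** The strongest reply is that a primary analysis can be inferred. Section 18.2 gives the contrast, the level, the sidedness and the power, and Section 18.4 lists a matching t-test. Summary statistics for continuous data would plausibly include the density change in each arm, and the regression already adjusts for baseline.

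Part of this stands. The implied test is a raw-change t-test, and its power is right. But an implied between-arm test is the comparison that Section 3.7 disclaims, summary statistics do not commit to an interval, and the regression yields only another between-arm coefficient.

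A reader might go further and infer that the untransformed analyses are wrong, so that log fold change must be used for every between-arm test. The documents do not support that. Section 18.2 defines an absolute difference in mean change, and doubling enters only as its approximate justification. The simulation in step 5 takes equal fold change as its null, so the log ratio holds 5% there by construction; step 6 shows the reverse. The planned baseline-adjusted regression holds its level under one assumed model and not under the other, and nothing in the documents says which applies.

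**Conclusion.** The concern holds as a mismatch between objective and inference. The objective concerns each regimen; the powered and tested quantity is a difference between non-randomised arms; and no per-arm estimate of the density change with a confidence interval is planned. This rests on the text alone and needs none of the assumed values.

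The scale issue is secondary and conditional. Where both fold changes are equal, an unadjusted raw-change test rejects about 11–42% of the time at an assumed 2-fold baseline gap, but only 4–8% at 1.25-fold, where the problem is small. The gap, the CVs, the correlations and the log-scale SDs are all assumptions. The per-arm ratio intervals rest on the assumed log-ratio SD and on 18 evaluable pairs per arm.

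It should not be inferred that the 83% is miscalculated, that the trial is too small, or that one scale is uniquely correct. No choice of scale separates regimen from MHC-II status.

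**What to change.** In Section 18.4:
- Name as primary the paired within-patient change in each arm, with a 95% CI, on one scale fixed before any density is read. Because the target is justified as a doubling, the geometric mean ratio is a natural choice, with an offset for zeros set in advance. Report the absolute change in counts/mm2 alongside it.
- Label any between-arm comparison secondary and descriptive, and state that regimen and MHC-II status are confounded. Report it on both the absolute and ratio scales, together with the planned baseline-adjusted regression, and interpret it cautiously if these disagree.

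In Section 18.2, keep the sample size, state that the 83% applies to the between-arm contrast on raw change, and add the per-arm precision from step 3 with its assumed SDs.

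The cost is a few sentences, a little more analysis and a pre-set rule for zeros. Patients, biopsies and visits do not change.
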